Transition to oral therapy may occur when the subject is considered clinically stable and able to take oral medication. If clinically indicated, some subjects may begin therapy with oral medication. If this occurs, a loading dose of POS 300 mg BID will be taken for the first day only. Subjects who are randomized to receive reference product (VOR Oral) will receive a double-dummy tablet with appearance consistent with POS tablet when transition to oral therapy.

IV infusions will be masked to blind the differences in appearance of study drug. Matching placebo infusions of 5% dextrose in water will be used for the additional daily doses in subjects randomized to POS to make the number of infusions per day (2) similar in the 2 treatment arms.

Reference Product:

- VOR IV Loading dose (Day 1): 6 mg/kg of body weight administered IV Q 12 hour (BID).
- VOR IV Maintenance dose (Beginning on Day 2): 4 mg/kg of body weight administered IV Q 12 hours (BID).
- VOR Oral (through Week 12): VOR oral capsule 200 mg BID to begin following transition from VOR IV.

Transition to oral therapy may occur when the subject is considered clinically stable and able to take oral medication. If clinically indicated, some subjects may begin therapy with oral medication. If this occurs, a loading dose of VOR 300 mg BID will be taken for the first day only. Subjects who are randomized to receive investigational product (POS Oral) will receive a double-dummy capsule with appearance consistent with VOR capsule when transition to oral therapy.

IV infusions will be masked to blind the differences in appearance of study drug.

STATISTICAL METHODS:

Type of Blinding: Double-Blind, Double-Dummy (for Oral Administration)

Only the investigational pharmacists or qualified medical personnel responsible for preparing the study drug will have knowledge of the treatment identity and will prepare study medications according to the protocol guidelines; all other study personnel will be blinded to study treatment. The unblinded pharmacists will not be involved in any post-treatment assessments for the subjects enrolled in this trial. Preparation of IV study therapy will be done by study personnel who are not otherwise involved in the clinical assessment (efficacy and safety assessments) of the subject. In order to maintain the blind, preparation of the intravenous study drugs must be performed by someone other than the persons who will evaluate the subject for clinical response and presence of adverse experiences.

IV infusions will be masked to blind the appearance of the IV study drugs. Matching placebo infusions of 5% dextrose will be used for the additional daily doses to make the number of infusions per day (2) similar in both treatment arms.

Oral POS tablets and oral VOR capsules will be administered using a double-dummy, double-blind method to blind study personnel and subjects as to the assigned treatment arm. Oral VOR will be given as over-encapsulated tablets with each capsule containing 100 mg of VOR or a placebo to VOR. The POS oral tablet will also be blinded by use of a dummy tablet with each tablet containing 100 mg of POS or a placebo to POS.

As VOR labeling recommends, dosage adjustment based upon hepatic insufficiency will be made. Appropriate dosing modifications will be included in the trial design in a blinded fashion. There is no planned dose reduction or dose adjustment of POS IV or POS oral tablet or POS dummy tablet.

This study will be conducted using in-house blinding procedures.

The primary hypothesis will be evaluated through Day 42 and the additional efficacy and safety data will be evaluated at Week 12, and 4 weeks following the Week 12 visit. All subjects will be followed for the entire study duration. For the final analyses, all data will be screened, discrepancies resolved, and protocol violators identified before the data are unblinded. All data-handling guidelines and actions will also occur prior to data unblinding according to sponsor's SOP for double-blind studies with in-house blinding.

Subject Replacement Strategy: Subjects will not be replaced in this study.

Randomization: Subjects will be randomly assigned (in a 1:1 ratio) to receive either POS or VOR according to a computer-generated randomization schedule using the interactive voice response system (IVRS).

Stratification: Subjects will be stratified prior to treatment assignment by risk status for mortality/poor outcome.

High Risk: Any one of the following are present at Baseline or in the patient's medical history:

- Allogeneic hematopoietic stem cell transplant (HSCT).
- Relapsed leukemia, undergoing salvage chemotherapy.
- Liver transplant recipients [12].

Not High Risk: Any other eligible subject (none of the high-risk criteria are present at Baseline or in the subject's medical history)

Data Sets to be Analyzed: The primary analysis will be performed on the ITT population. The ITT population consists of all randomized subjects who have received at least one dose of study drug. Secondary analyses will be based on the FAS population which includes subjects with confirmed proven or probable IA (based on 2008 modified EORTC/MSG definitions) and who: 1) receive at least one dose of study treatment; 2) have at least one post-randomization observation for the analysis endpoint subsequent to at least one dose of study treatment; 3) have baseline data for those analyses that require baseline data. Safety analyses will be based on the all-patients-as-treated (APaT) population, which includes all subjects who received at least one dose of study treatment. The FAS population consists of all randomized subjects who have at least one post-randomization observation for the analysis endpoint subsequent to at least one dose of study treatment (and have baseline data for those analyses requiring baseline data).

Sample Size: Approximately 600 subjects will be enrolled in this study, receive study drug and be randomly assigned in a 1:1 ratio to receive either POS or VOR. This sample (approximately 300 randomized subjects in each azole arm) will have ~ 82.7% power (with 1-sided alpha=0.025) to show non-inferiority of POS compared to VOR using a 10% margin assuming an all-cause mortality through Day 42 of 23% for both treatment groups. This assumed rate is based on a meta-analysis of historical VOR mortality data [27]. If the criteria for non-inferiority are met, then a superiority analysis of POS over VOR will be assessed.

Efficacy Analysis:

The primary analysis will be performed on the ITT population, which consists of all randomized subjects who received at least one dose of study treatment.

The primary endpoint in this study is all-cause mortality through Day 42 and which will be compared between the POS arm and the VOR arm for the ITT population. The primary analysis will be assessed using a non-inferiority margin of 10%. Ninety-five percent Confidence Intervals (CI), adjusted for stratification factors for the difference in success rates (POS minus VOR) will be computed. If upper limit of that CI is less than 10%, then non-inferiority of POS will be declared. If non-inferiority is declared, then superiority of POS over VOR will be assessed and will be declared if the lower limit of the CI is greater than 0.

Secondary endpoints include the global clinical response at Week 6 and Week 12 in the FAS population, all-cause mortality through Day 42 and Day 84 in the FAS population and all-cause mortality through Day 84 in the ITT population. All will be evaluated using a similar methodology as that for the primary analysis.

Other endpoints (i.e., time to death [all causes] in the FAS population; and mortality due to IA at Weeks 6 and 12 in the FAS population) will also be analyzed. Adjudicated global clinical response Weeks 6 and 12 in subjects with possible, probable, or proven IA subjects (ITT population) will also be assessed as a secondary endpoint.

Survival will be assessed using a Kaplan Meier estimates and will be compared between the two arms using the Log-Rank test.

Other analyses: Sparse pharmacokinetic (steady state trough) sampling will be performed on all subjects throughout the treatment period. Data regarding food intake relative to posaconazole tablet administration will be collected and the effect of food on the steady state pharmacokinetics of posaconazole tablet will be evaluated. Plasma concentrations over time in individual subjects including adolescents will be evaluated including an evaluation of plasma concentrations at the time of adverse events. In subjects receiving IV study therapy, at the time of maximum concentration, data regarding ECG parameters will be evaluated. Exploratory analysis may be conducted on pharmacogenomic endpoints and their association with key efficacy and safety parameters at a later date, as data allow.

Safety Analysis: The incidence of serious adverse events (SAEs), incidence of treatment-emergent and treatment-related AEs (overall, treatment-related, and selected AEs of interest) as well as other safety endpoints will be summarized by treatment groups.

The analysis of safety results will follow a tiered approach. The tiers differ with respect to the analyses that will be performed. The following four categories are Tier 1 events:

- **Hepatic safety:** Elevated AST or ALT lab value that is ≥ 3 x the upper limit of normal (ULN) and an elevated total bilirubin lab value that is ≥ 2 x ULN and, at the same time, an alkaline phosphatase lab value that < 2 ULN, as determined by way of protocol-specified laboratory testing or unscheduled laboratory testing;
- **CNS and visual safety:** Treatment-emergent adverse events (TEAEs) related to CNS or visual disturbances. See [Section 8.5.2](#) for a list of terms;
- **Dermatologic reactions:** TEAEs including rash and photosensitivity rash;
- **Adrenal steroidogenesis:** TEAEs indicating adrenal insufficiency or temporally associated TEAEs of hypotension.

[figure not shown]
The following are Tier 2 events based on specific AE categories: (1) proportion of subjects with at least one adverse experience; (2) proportion of subjects with at least one drug related adverse experience; (3) proportion of subjects with at least one serious adverse experience; (4) proportion of subjects with at least one serious and drug related adverse experience; (5) proportion of subjects who discontinued study therapy due to an adverse experience. 95% confidence intervals (Tier 2) will be provided for between-treatment differences in the percentage of subjects with events; these analyses will be performed using the Miettinen and Nurminen method, an unconditional, asymptotic method.

The APaT population will be used to assess safety in this study. All patients who received at least one dose of study treatment will be included in the APaT population.

Pharmacogenetics: Exploratory analysis may be conducted on pharmacogenomic endpoints and their association with key efficacy and safety parameters at a later date, as data allow

eDMC: Safety will be monitored by the external Data Monitoring Committee (eDMC) on an ongoing basis and the eDMC will make recommendations to the Sponsor as appropriate.

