aspergillosis (Cavg at least 1250 ng/mL) will be more rapidly and more consistently achieved. In the strategy employed by this protocol, a sufficient number of subjects with well documented IA can be enrolled within a reasonable time, following treatment paradigms which reflect clinical practice and provide data to support the safety and efficacy of POS versus VOR in the treatment of patients who have suspected or documented aspergillosis.

Trial Design

Overview: This is a Phase 3, randomized, double-blind study of POS versus VOR in subjects with IA as defined by modified EORTC/MSG consensus criteria. Subjects with features consistent with proven, probable, or possible IA will be enrolled. All randomized subjects who receive at least one dose of study drug will be included in the primary ITT population. Subjects who are enrolled with a diagnosis of possible IA will undergo additional diagnostic work-up to confirm proven or probable IA post-randomization are to be included in the secondary FAS population.

At the time of study enrollment, subjects will be randomized to receive one of two possible treatment arms: POS or VOR for a maximum total duration of therapy of 12 weeks. In general, most subjects should receive the full 12 weeks of study therapy. Subjects will be randomized to POS or VOR in a 1:1 ratio. Overall, approximately 600 subjects will be enrolled, randomized and treated in the study will comprise the primary ITT population (approximately 300 ITT-eligible subjects per treatment arm). The study will also evaluate subjects whose diagnosis of proven or probable IA as confirmed by an independent Clinical Adjudication Committee (CAC) will comprise the secondary FAS study population. The FAS further requires subjects to have received at least one dose of study drug and have at least one post-randomization observation for the analysis endpoint subsequent to at least one dose of study treatment (and have baseline data for those analyses requiring baseline data).

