comprise the ITT dataset. In addition, subjects whose diagnosis of proven or probable IA is confirmed post-randomization by the CAC will comprise the FAS dataset. The CAC will adjudicate classification of the global clinical response to treatment (as per modified 2008 EORTC/MSG guidelines) at 6 weeks and at 12 weeks/end-of therapy (EOT) post-randomization. A successful global clinical response will be defined as an FAS-evaluable subject who is judged by the CAC to be alive and have a complete or partial response at the time points of interest. The CAC will also adjudicate IFI-attributable mortality through Day 42 and Day 84 in subjects as data allow.

The primary analysis will test for non-inferiority of all-cause mortality for POS compared to VOR through Day 42. The primary analysis will be conducted in the ITT population.

Secondary analyses will include a comparison of global clinical response at Week 6 in the FAS data set. The FAS population consists of all randomized subjects who have confirmed proven or probable IA (based on modified 2008 EORTC/MSG definitions) post-randomization and who receive at least one dose of study treatment and have at least one post-randomization observation for the analysis endpoint subsequent to at least one dose of study treatment (and have baseline data for those analyses requiring baseline data). Additional secondary analyses include all-cause mortality through Day 42 and Day 84 in the FAS population, global clinical response at both Week 6 and Week 12 in the FAS population and all-cause mortality through Day 84 in the ITT population. Safety will also be evaluated for both treatment groups using an All-Patients-as-Treated (APaT) population, which includes all subjects who received at least one dose of study treatment.

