5.2 Subject Population Rationale

The primary study population is the intent-to-treat (ITT) population, which includes all randomized subjects who received at least one dose of study drug. However, of further interest in this study is the subset of subjects with a diagnosis of proven or probable invasive aspergillosis (IA) based on modified 2008 EORTC/MSG definitions [10]. Subjects with possible IA may also be enrolled into the study with further evaluation of proven or probable IA, which must be confirmed post-randomization to be included in the FAS analysis on the secondary endpoints. (Note, inclusion in the FAS further requires subjects have at least one post-randomization observation for the analysis endpoint subsequent to at least one dose of study treatment [and have baseline data for those analyses requiring baseline data]).

Subjects with proven invasive fungal infection (IFI) will have confirmed infection based upon detection of the fungus by histological analysis or culture of a specimen taken from sterile material from a site of infection. Subjects with probable IFI will require the presence of appropriate host factors, clinical criterion, and a mycological

criterion including both direct tests and indirect tests including serum galactomannan antigen detection. Host factors include: recent history of neutropenia temporally related to a fungal disease (Any duration of neutropenia is also acceptable for possible criteria in this study), receipt of an allogeneic HSCT, treatment with T-cell immune suppressants, prolonged corticosteroid use, and inherited severe immunodeficiency. See [Appendix 3](#) for the criteria for diagnosing invasive aspergillosis.

Subjects selected for this study will be 13 years of age or greater. Subjects between 13 and 14 years of age must weigh ≥ 50 kg [110lb].

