^a Subjects will begin IV study drug and then step down/transition to oral study drug. If clinically indicated, some subjects may begin study drug with oral therapy instead of IV therapy.
^b Day 1 refers to the first day of subject taking either IV or Oral therapy. Subjects will only take one formulation, either IV or oral at a time
^c The planned duration of study therapy is 12 weeks (84 days) with a maximum allowable duration of up to 98 days. IV=intravenous; POS=posaconazole; VOR=voriconazole

Diagnostic, attributable mortality, and efficacy data from all subjects will be reviewed by an independent CAC who will be blinded to the assigned treatment arm. The CAC will determine acceptability of the diagnostic criteria of a proven or probable IFI according to modified MSG/EORTC consensus criteria [9]. Subjects who are randomized receive at least one dose of study drug and whose diagnosis of proven or probable IA is confirmed by the CAC will comprise the FAS dataset. (The FAS further requires subjects to have received at least one dose of study drug and have at least one post-randomization observation for the analysis endpoint subsequent to at least one dose of study treatment [and have baseline data for those analyses requiring baseline data]). The CAC will adjudicate the global clinical response to

treatment (as per 2008 EORTC/MSG guidelines) at 6 weeks and at 12 weeks post-randomization. A successful global clinical response will be defined as an FAS-evaluable subject who is judged by the CAC to be alive and have a complete or partial response at the time point of interest. The CAC will also adjudicate IFI-attributable mortality through Day 42 and Day 84 in subjects as data allow.

The primary analysis will be performed on the ITT population. The ITT population consists of all randomized subjects who received at least one dose of study treatment.

The primary endpoint in this study is all-cause mortality through Day 42 between the POS arm and the VOR arm for the ITT population. The primary analysis will be assessed using a non-inferiority margin of 10%. Ninety-five percent Confidence Intervals (CI), adjusted for stratification factors for the difference in success rates (POS minus VOR) will be computed. If upper limit of that CI is less than 10%, then non-inferiority of POS will be declared. If non-inferiority is declared, then superiority of POS over VOR will be assessed and will be declared if the lower limit of the CI is greater than 0.

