8.4.1 Efficacy Analysis Populations

The Intention to Treat (ITT) population will serve as the primary population for the analysis of all-cause mortality through Day 42 in this study. The ITT population consists of all randomized subjects who received at least one dose of study treatment.

The Full Analysis Set (FAS) population will serve as the secondary population for the analysis of efficacy data in this study. The FAS population consists of all randomized subjects who have been classified as having proven or probable IA (based upon independent adjudication assessment using the modified 2008 EORTC/MSG definitions), and receive at least one dose of study drug.

Subjects will be included in the treatment group to which they are randomized for the analysis of efficacy data using the ITT and FAS populations. Details on the approach to handling missing data are provided in [Section 8.5](#) Statistical Methods.

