8.5.1 Statistical Methods for Efficacy Analyses

All-Cause Mortality

The primary endpoint, corresponding to the primary trial objective, is all-cause mortality through Day 42 in subjects in the ITT population.

The primary analysis is to compare the POS arm to the VOR arm. The difference in mortality rate between arms (POS minus VOR) and the associated 95% confidence interval (CI) on the difference will be calculated using Miettinen and Nurminen's method [13] stratified by risk for mortality/poor outcome (high risk, not high risk). If the upper limit of that CI is less than 10% (the non-inferiority margin), then non-inferiority of POS will be declared. If non-inferiority is declared, it can be further concluded that POS is superior to VOR if the lower limit of the CI exceeds zero. Due to the principle of closed testing, no adjustment for multiplicity is required since non-inferiority can always be concluded whenever the data also supports superiority. Summary statistics and a tabulated treatment comparison will be provided.

Other secondary endpoints include all-cause mortality through Day 42 and Day 84 for the FAS population and will be evaluated using similar methodology as will be used for the primary endpoint in the ITT population.

Mortality will be evaluated through Day 42 and through Day 84 with no time window applied either before or after the target day.

Survival will also be assessed using Kaplan-Meier methodology and compared between the two arms using the Log-Rank test stratified by risk for mortality/poor outcome (high risk, not high risk).

Proportion Of Subjects Achieving Global Clinical Response

A secondary endpoint is global clinical response (partial or complete response defined by the 2008 MSG/EORTC criteria) at 6 weeks post-randomization in the FAS population.

The analysis is to compare the POS arm to the VOR arm. The difference in proportions between arms (POS minus VOR) and the associated 95% confidence interval (CI) on the difference will be calculated using Miettinen and Nurminen's method [13] stratified by risk for mortality/poor outcome (high risk, not high risk). For the analysis, missing or unable to determine responses will be considered as failures.

An assessment between the two treatment arms will be performed on ITT subjects that are excluded from the FAS, looking at potentially key baseline prognostic factors, such as the stratification variable of risk status for mortality/poor outcome.

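### The FAS is defined two ways: 2.0, 5.2 and 7.1 require a post-randomization endpoint observation that 8.4.1 does not, so unassessed confirmed-IA patients may be dropped rather than counted as response failures

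*Combined protocol and SAP*

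**What the plan says.** Section 8.4.1 sets two conditions for the FAS, an adjudicated diagnosis and at least one dose: "The FAS population consists of all randomized subjects who have been classified as having proven or probable IA".

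Five other places add a third condition, an endpoint observation after dosing, together with baseline data where the analysis needs them:

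- 2.0, Trial Design overview: "The FAS further requires subjects to have received at least one dose of study drug and have at least one post-randomization observation".
- 2.0, paragraph on secondary analyses: "who receive at least one dose of study treatment and have at least one post-randomization observation for the analysis endpoint".
- 2.0, Data Sets to be Analyzed: the condition is item 2 of a numbered list and is repeated in the closing sentence, "The FAS population consists of all randomized subjects who have at least one post-randomization observation for the analysis endpoint".
- 5.2: "inclusion in the FAS further requires subjects have at least one post-randomization observation for the analysis endpoint".
- 7.1: "have at least one post-randomization observation for the analysis endpoint subsequent to at least one dose of study treatment".

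On missing data for global clinical response, 8.5.1 says "For the analysis, missing or unable to determine responses will be considered as failures". Table 13 repeats this for the FAS at Weeks 6 and 12. Section 8.0 states that there will be no separate SAP.

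**The concern.** Whether a patient belongs to the FAS is settled before the missing-equals-failure rule is applied. If membership requires an endpoint observation, a treated patient with confirmed IA and no response observation is never in the set to which the rule applies. If 8.4.1 governs, the same patient is in the denominator as a failure. The two readings therefore give different denominators for two named secondary endpoints, and the observation-required reading excludes patients on a post-randomization event.

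The closing FAS sentence in Data Sets to be Analyzed also leaves out the diagnosis. That omission is editorial, since the same paragraph says "Secondary analyses will be based on the FAS population which includes subjects with confirmed proven or probable IA".

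**Working it through.** **Who is affected.** Several provisions narrow the group:

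- Death is a failure category in Table 11 (7.7.1.2), so a death is an observed outcome.
- Response is assessed at early discontinuation of therapy (7.6, item 23).
- The Week 6 and Week 12 visits are required of all treated patients (7.2).
- Mortality is followed to Day 114 whatever the treatment status (2.2, footnote u), so FAS mortality is much less exposed than response.

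What remains is mainly patients lost to follow-up, or withdrawing consent, before any response assessment.

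**Check against the plan's own figures.** The unstratified Miettinen-Nurminen interval (Appendix 7) for 78/300 v 69/300 comes out at -3.9 to 9.9, as printed in 8.7.2. The 82.7% power for 23% v 23%, 300 per arm, a 10% margin and one-sided alpha 0.025 is reproduced with the Farrington-Manning variance. It concerns ITT mortality and does not depend on the FAS.

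**Inputs for the illustration.** Let r be the response rate among observed patients, taken as equal in both arms, and m1 and m2 the proportions of confirmed-IA patients with no observation on POS and VOR. For r, I use two VOR rates cited in 5.1: 38.9% (end of therapy, isavuconazole trial) and 53% (12 weeks, open-label trial against amphotericin B). The documents give neither m nor the FAS size, so m and 200 per arm are assumptions.

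**Formula.**

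- Unobserved patients removed: each arm's rate is r, so the difference is 0.
- Unobserved patients counted as failures: the rates are r(1 - m1) and r(1 - m2), so POS minus VOR is -r(m1 - m2).
- The two definitions therefore differ by r(m1 - m2) in size.

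| m1 v m2 | r = 38.9% | r = 53% |
|---|---|---|
| equal | 0 | 0 |
| 2% v 1% | 0.389 × 1 = 0.39 points | 0.53 × 1 = 0.53 points |
| 10% v 5% | 0.389 × 5 = 1.9 points | 0.53 × 5 = 2.7 points |

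**With intervals** (r = 38.9%, assumed 200 per arm, responders rounded to whole patients, unstratified Miettinen-Nurminen 95% CI):

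| Unobserved, POS v VOR | Removed | Counted as failures |
|---|---|---|
| 4 v 2 | 76/196 v 77/198: -0.1 (-9.7 to 9.5) | 76/200 v 77/200: -0.5 (-10.0 to 9.0) |
| 20 v 10 | 70/180 v 74/190: -0.1 (-10.0 to 9.9) | 70/200 v 74/200: -2.0 (-11.4 to 7.4) |

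The small non-zero differences in the Removed column come from rounding.

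**Arm-level rates** change even when missingness is balanced: 0.389 × 0.98 = 38.1% with 2% unobserved, and 0.389 × 0.90 = 35.0% with 10%.

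**The case against.** The best reply is that Section 8 is the analysis plan and settles the matter. Section 8.0 describes it as the analysis strategy, 10.3.2 refers to it as the statistical analysis plan, and the amendment summary gives clarification of the FAS for analysis as the reason for editing 8.4.1. Sections 8.4.1 and 8.5.1 and Table 13 agree with one another, so the remaining wording looks like edits that were not carried through. That is probably the intent. But there is no precedence clause, and five current places still state the other rule. The synopsis does put data-handling decisions before unblinding, which guards against a choice driven by results. It does not say which definition those decisions will use.

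A second reply is that an observation for the endpoint could be read broadly. Signs, symptoms and galactomannan are collected from Day 3. If any component counts, nearly every treated patient qualifies, and incomplete cases become undeterminable and hence failures. It is equally unclear whether a patient assessed at Week 6 but not Week 12 stays in at Week 12. The text settles neither point, so the affected group could be smaller or larger than described above. This is a further reason to drop the condition.

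A third reply is that 10% v 5% unobserved has no support in the documents. That is correct. It is shown only as a range, and the 2% v 1% case shifts the difference by about half a point or less.

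**Conclusion.** The concern holds. The current text gives two FAS definitions that treat unassessed, confirmed-IA patients in opposite ways, and no rule ranks them. The effect is confined to reported secondary estimates, chiefly Week 6 and Week 12 global clinical response. These get 95% CIs and no confirmatory test (8.5, 8.6, Table 13). Under the assumptions above, the treatment difference moves by 0 to 2.7 points, and by about half a point or less if missingness is as low as 2% v 1%. At 200 per arm the interval is about 19 points wide. These sizes rest on assumed missingness, an assumed FAS size and equal response among observed patients. The textual conflict rests on none of them. The correction should be made because it is cheap and because a population needs a single definition.

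**What to change.** Make 8.4.1 the only definition of the FAS. In 2.0 (Trial Design overview, paragraph on secondary analyses, Data Sets to be Analyzed), 5.2 and 7.1, delete the endpoint-observation and baseline-data condition and refer to 8.4.1. Delete the closing FAS sentence of Data Sets to be Analyzed. Add to 8.5.1 that FAS patients with no response assessment at all count as failures. This largely restates the existing rule but removes any doubt about its reach.

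The cost is wording only, with no change to sample size, the primary analysis or data collection. Reported FAS response rates may be slightly lower than under the observation-required definition, by the arm-level amounts worked out above.
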